5.4 Blinding Procedures

This is a double-blind study; neither the patients nor the Investigator will be aware of the treatment assignment for the patients. Blinding will be maintained throughout the study by the use of active and placebo treatment vials of similar appearance and volume-matched dosing.

With the exception of the person responsible for preparing and administering the randomization codes, the staff of the third-party vendor responsible for packaging study drug, the staff of third party vendors processing the PK samples and data, and quality assurance auditors where necessary, all clinical and nonclinical staff will remain blinded to the treatment allocation until after the study database is locked and has completed unblinding.

Blinding, unblinding, and management of the randomisation codes will proceed according to an appropriate manual provided separately.

5.5 Reasons for Patient Withdrawal

All patients have the right to withdraw from treatment or from the study at any time, for any reason, without prejudice. The Investigator may, but is not required to, discontinue any patient's study drug treatment for reasons of non-efficacy of the study drug or other reasons. The Investigator will notify the CRO and Sponsor of all decisions regarding withdrawal of the patient from treatment or from the study.

Patients will be encouraged to remain in the study and on treatment so long as there are no overarching safety concerns about their continued participation.

5.6 Rhinosinusitis or Asthma Exacerbation as Withdrawal Criterion

If there are safety concerns, the Investigator may, but is not required to, discontinue the patient's study drug treatment for lack of efficacy if the patient experiences a rhinosinusitis exacerbation that results in 1 or more of the following:

- Hospitalization due to rhinosinusitis
OR
- Treatment with systemic steroids for > 5 days
OR
- Decision to proceed to surgery for removal of nasal polyps.

The Investigator may, but is not required to, discontinue the patient's study drug treatment for lack of efficacy if the patient experiences an asthma exacerbation as defined as a deterioration of asthma that results in 1 of the following:

- Asthma requiring prolonged treatment increase of approximately 4 times the baseline dose of ICS or the physician-prescribed addition of additional controllers
OR
- Hospitalization due to asthma

Even if the patient's study drug treatment is discontinued due to treatment failure, the patient should be encouraged to remain in the study and all study procedures should be completed unless the patient withdraws consent or is lost to follow-up.

Note: Patients may experience symptoms of decreased asthma control that do not reach the level of the exacerbation criteria but warrant concern from the clinical site. These "loss of control events" are defined as follows: An increase of 6 or more reliever occasions (1 puff = reliever occasion) in a 24-hour period for ≥ 2 consecutive days along with decreased peak flow will fulfill the definition of "loss of asthma control." Loss of asthma control events should be flagged in the eCRF and may be further recorded as an AE (worsening of specific symptoms). Patients experiencing a loss of asthma control may remain in the study but the patient should be instructed to contact the site for management of symptoms.

5.7 Other Reasons as Withdrawal Criteria

The Investigator may also discontinue a patient's study drug treatment or study participation for reasons including, but not limited to, the following: AEs deemed by the Investigator to preclude continued study

Suzhou Connect Biopharmaceuticals, Ltd

Protocol CBP-201-WW003

Investigational Drug: CBP-201

21 December 2021

participation, protocol violations, withdrawal of consent, loss to follow-up, death of patient, or termination of the study by the Investigator or Sponsor.

Patients who develop any related grade 2 or higher cardiovascular, respiratory, or ophthalmic TEAE or any related grade 3 or higher TEAE involving other organ systems must be discontinued from further study drug treatment and monitored until resolution or stabilization.

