3.5 Discontinuation and Study Stopping Rules

Dosing for any individual patient will be stopped if the patient experiences a drug-related SAE or a drug-related significant nonserious adverse event (AE), which, in the opinion of the Investigator, physician, or Sponsor's medical representative, warrants discontinuation of the study for that patient's well-being.

Patients should be encouraged to remain in the study even if they have discontinued study drug treatment due to treatment failure.

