8.5 Assessment of Adverse Event Severity

The investigator may use the CTCAE Version 5.0 to assist in the determination of severity and clinical significance. The following represents CTCAE grading of AE severity:

- **Grade 1 / Mild:** asymptomatic or mild symptoms or clinical or diagnostic observations only or intervention not indicated
- **Grade 2 / Moderate:** minimal, local or non-invasive intervention indicated or limiting age-appropriate instrumental activities of daily living (ADLs). Instrumental ADLs refer to preparing meals, shopping for groceries or clothes, using the telephone, managing money etc

- **Grade 3 / Severe or Medically Significant But Not Immediately Life-threatening:** hospitalization or prolongation of hospitalization indicated or disabling or limiting self-care ADLs. Self-care ADLs refer to bathing, dressing and undressing, feeding self, using the toilet, taking medications and not bedridden
- **Grade 4 / Life Threatening Consequences:** urgent intervention indicated.
- **Grade 5 / Death Related to AE**

AEs not listed by the CTCAE will be graded as follows:

- **Grade 1 / Mild:** discomfort noticed but no disruption of normal daily activity
- **Grade 2 / Moderate:** discomfort sufficient to reduce or affect daily activity
- **Grade 3 / Severe:** inability to work or perform normal daily activity
- **Grade 4 / Life Threatening:** represents an immediate threat to life
- **Grade 5 / Death**

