8.6 Adverse Event of Special Interest

An AESI is an AE (serious or nonserious) of scientific and medical concern specific to the Sponsor's product or program, for which ongoing monitoring and immediate notification by the Investigator to the Sponsor is required. Such events may require further investigation in order to characterize and understand them. These events should be marked "AESI" in the EDC. Adverse events of special interest may be added or removed during a study by protocol clarification note or amendment.

AESIs for this study:

- Conjunctivitis
- Keratitis
- Anaphylaxis (definition below)
- AE of injection site reaction lasting >24 hours (guidance below)
- AST/ALT elevated >5X ULN
- Parasitic and opportunistic infections
- Pregnancy
- Symptomatic overdose (i.e. overdose of study drug resulting in an adverse event)

Conjunctivitis and keratitis have been subjects of interest in the dupilumab experience. (Akinlade 2019) reported that in the combined dupilumab experience in atopic dermatitis patients (n = 1047) there were a total of 90 (8.6%) patients reporting at least 1 AE of “conjunctivitis” while those patients in the placebo group (n = 517) reported 11 (2.1%) such events. Conjunctivitis AEs were mostly mild to moderate in severity with severe events reported in ≤ 0.5% of the dupilumab combined group vs. ≤ 0.3% of the placebo group. Two patients in the dupilumab group permanently discontinued study drug treatment due to a conjunctivitis event. Onset typically occurred during Weeks 4 to 8 and events became less common with long-term treatment. Conjunctivitis was more common in those patients with severe AD at baseline, those with a prior history of conjunctivitis and those with higher baseline levels of TARC and IgE. Pooled dupilumab data suggested that conjunctivitis incidence may decrease with higher trough concentrations of dupilumab.

This pattern was not observed in dupilumab studies in other indications including asthma and CRSwNP.

Due to the dupilumab experience in atopic dermatitis, ophthalmic adverse events of “conjunctivitis” and “keratitis” will be considered AEs of Special Interest (AESI) and may be evaluated by an ophthalmologist if deemed advisable by the Investigator or Sponsor. The appropriate treatment should be rendered until resolution.

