8.7 Mandatory Early Termination

Using CTCAE Version 5.0, patients who develop any related grade 2 or higher cardiovascular, respiratory or hematologic (example eosinophilia) TEAE or any related grade 3 or higher TEAE involving other organ systems must be discontinued from further study drug treatment and monitored until resolution or stabilization.

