- AEs by SOC and PT
- Serious AEs by SOC and PT
- TEAEs by SOC and PT
- TEAEs by SOC and PT for Subjects with Rescue Medications
- TEAEs by decreasing frequency of PT
- TEAEs by SOC, PT, and maximum severity
- TEAEs of grade 3 or higher by SOC and PT
- TEAEs related to study drug by SOC and PT
- TEAEs related to study procedure by SOC and PT
- Any TEAEs occurring more than 5% of subjects in overall
- Serious TEAEs by SOC and PT
- TEAEs leading to death by SOC and PT
- TEAEs leading to study drug discontinuation by SOC and PT
- TEAEs leading to study drug interruption by SOC and PT

By-subject listings of corresponding adverse events summary will also be provided.

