#### **4.15 Changes in the Conduct of the Study or Planned Analysis**

Enrollment of Sponsor's Phase 2 trial evaluating CBP-201 in chronic rhinosinusitis with nasal polyps, which commenced in June 2021, has faced challenges due to the macroenvironment -- namely ongoing impact of COVID and the current Russia-Ukraine conflict throughout [Eastern] Europe.

Therefore, the Sponsor has made the decision to terminate this trial early, and the planned analyses have been changed to focus on safety assessments.

For the efficacy endpoints, only descriptive summary statistics will be provided for the co-primary efficacy assessments. No formal hypotheses will be tested due to the small sample size. No sensitivity or subgroup analyses will be performed. All other efficacy assessments will be listed except percentage of maxillary sinus volume occupied by disease on CT and Lund-Mackay Computed Tomography scores.

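### Protocol 5.7 and 8.7 state the same mandatory study-drug stop with different grade 2 organ-system lists, so they disagree on related grade 2 ophthalmic and hematologic events

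*Protocol*

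**What the plan says.** Protocol 5.7 (Other Reasons as Withdrawal Criteria) covers "Patients who develop any related grade 2 or higher cardiovascular, respiratory, or ophthalmic TEAE" and then adds that "any related grade 3 or higher TEAE involving other organ systems must be discontinued from further study drug treatment".

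Protocol 8.7 (Mandatory Early Termination) names CTCAE version 5.0 as the grading scale and covers "patients who develop any related grade 2 or higher cardiovascular, respiratory or hematologic (example eosinophilia) TEAE". It has the same grade 3 clause for other organ systems and the same compulsory action.

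Three other protocol sections bear on the point:

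- **3.5** requires dosing to stop for a drug-related SAE, or for a significant nonserious drug-related event that the investigator, physician or sponsor's medical representative thinks warrants it. It names no organ system and no grade.
- **8.5** includes in grade 2 any event with "minimal, local or non-invasive intervention indicated or limiting age-appropriate instrumental activities of daily living".
- **8.6** makes conjunctivitis and keratitis adverse events of special interest (AESIs). It says they "may be evaluated by an ophthalmologist if deemed advisable by the Investigator or Sponsor. The appropriate treatment should be rendered until resolution", and it does not mention the stop in 5.7.

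On the analysis side, SAP 4.12.2 plans a table of "TEAEs leading to study drug discontinuation by SOC and PT". SAP 4.15 reports that, after the decision to terminate early, "the planned analyses have been changed to focus on safety assessments".

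**The concern.** This is one safety rule written twice with two different lists. Neither section cites the other or says which prevails, and both are current protocol text rather than entries in a change log.

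The likeliest failure is an eye event handled through the adverse event chapter. The investigator reads 8.6, which says to treat, and then 8.7, which does not list ophthalmic events at grade 2. The patient goes on being dosed although 5.7 requires a stop. The reverse can happen with a blood event at a site that works from the withdrawal criteria in section 5.

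The same conduct would then comply with one section and deviate from the other. Whether such an event appears in the table of events leading to discontinuation would depend on which page the site used. In a trial whose remaining analysis is mainly safety, that makes the discontinuation counts harder to interpret.

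**Working it through.** The plan gives no figure to reproduce. The check sets the two rules side by side for related treatment-emergent events.

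**Inputs.** The grade 2 lists and grade 3 clauses of Protocol 5.7 and 8.7, with grades 1 to 5 as in Protocol 8.5. Organ systems are grouped into five classes: the four named in either list, plus all others.

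| Related event | 5.7 | 8.7 | Agree? |
|---|---|---|---|
| Grade 1, any class | no compulsory stop | no compulsory stop | yes (5 cells) |
| Grade 2 cardiovascular | stop | stop | yes |
| Grade 2 respiratory | stop | stop | yes |
| Grade 2 ophthalmic | stop | no compulsory stop | **no** |
| Grade 2 hematologic | no compulsory stop | stop | **no** |
| Grade 2, all other | no compulsory stop | no compulsory stop | yes |
| Grades 3 to 5, any class | stop | stop | yes (15 cells) |

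Total cells: 5 classes × 5 grades = 25. Agreeing: 5 + 3 + 15 = 23. Differing: 25 − 23 = 2. This count describes the scope of the mismatch. It says nothing about how often such events occur.

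**Does another section settle the two cells?** Section 3.5 does not, because it turns on opinion and sets no grade. Section 8.6 does not, because it deals with treatment and notification. The SAP sets no stopping threshold.

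**Can the two cells be occupied?**

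- *Ophthalmic.* Under the general wording of 8.5, a related conjunctivitis or keratitis that needs only local treatment can be grade 2.
- *Hematologic.* SAP Appendix E shows a dash at grade 2 for eosinophilia, so the one example in 8.7 has no grade 2 laboratory criterion in that table. Anemia does have one (hemoglobin below 10.0 down to 8.0 g/dL), as do low platelet, neutrophil and white cell counts. The cell is therefore not empty.

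**The case against.** The strongest reply is that the sections do not give contradictory orders. Each says when dosing must stop, and neither forbids stopping in other cases. A site bound by the whole protocol complies with both by stopping whenever either applies, so harm needs a site that reads only one section. That is correct. But the protocol does not tell sites to combine the lists, and a reader of one section has no cue to look for the other.

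Other points reduce the practical weight:

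- Protocol 8.6 says the conjunctivitis pattern seen with dupilumab in atopic dermatitis was not observed in other indications, including this one. That argues for few eye events, but the sponsor kept conjunctivitis and keratitis as AESIs here.
- The event-specific CTCAE criteria for conjunctivitis and keratitis are not in the documents, so their grade 2 status rests on the general definition in 8.5.
- Treating an eye event and stopping study drug are compatible. Section 8.6 omits the stop; it does not contradict it.
- AESI notification, the discretionary stop in 3.5 and the data and safety monitoring board make it less likely that a significant event goes unreviewed. None of them sets the threshold, and hematologic events as a class are not AESIs.
- The trial is being terminated early, so corrected wording may come too late to affect dosing. The documents do not say whether dosing had ended.

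These points limit the likely consequences. They do not remove the mismatch.

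**Conclusion.** The concern holds: the protocol is wrong as written. Sections 5.7 and 8.7 set different compulsory stopping thresholds for related grade 2 ophthalmic and related grade 2 hematologic events, and agree everywhere else. The conclusion rests only on the current text of the two sections, and confidence is high.

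The effect on patients and on the discontinuation table cannot be sized. Sample size and the efficacy analyses are not touched. Because this is a compulsory safety rule and the correction is cheap, it should be fixed, but it is narrow in scope.

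**What to change.** Put one identical list in 5.7 and 8.7. The default should be the union: related grade 2 or higher events in the cardiovascular, respiratory, ophthalmic or hematologic systems, and related grade 3 or higher events in any other system. Full compliance with both sections already requires this. If the clinical team did not intend one of the systems, it should document that and remove it from both places.

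Have one section refer to the other, add a pointer to the rule in the conjunctivitis and keratitis text of 8.6, and send sites a clarification. While the text is open, reconsider the eosinophilia example, given the dash at grade 2 in SAP Appendix E.

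The cost is a wording change in two sections, one pointer and a site notice. The union may lead to a few more compulsory discontinuations. If dosing has ended, a sentence in the study report stating which rule sites applied is enough.

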5.8 Handling of Withdrawals

When a patient is withdrawn from study drug treatment or is withdrawn from the study, the reason(s) for withdrawal must be recorded by the Investigator in the patient's medical record and eCRF.

Whenever possible, patients who withdraw from the study prematurely will undergo all end-of-study assessments, ie, Early Termination Visit procedures. Patients who fail to return for final assessments will be contacted by the site in an attempt to have them comply with the protocol. The only exception to this schedule is if patients withdraw from the study prior to randomization at Visit 2. If a patient withdraws or is withdrawn from the study prior to study drug treatment, this will be considered a screen failure and only the following information need be collected at their last visit: AEs, review of concomitant medications, return of patient diary, review of diary data.

It is vital to obtain follow-up data or continue visits for any patient withdrawn from study drug treatment because of an AE or SAE. Every effort must be made to undertake protocol-specified safety follow-up procedures. If a patient is discontinued from the study drug treatment because of an AE, this event will be followed until resolution or stabilization.

When possible, last observations of clinical data will be carried forward for analysis from all patients who are withdrawn from study drug treatment prematurely.

5.9 Replacements

Patients who withdraw or are withdrawn from the study will not be replaced.

5.10 Sponsor's Termination of Study

Although the Sponsor has every intention of completing the study, the Sponsor reserves the right to discontinue the study at any time for clinical or administrative reasons.

6 STUDY VISITS

Patients are requested to delay using bronchodilators prior to each visit where spirometry is performed (SABA for at least 6 hours, twice-daily LABAs or combination products for at least 12 hours, once-daily bronchodilators, or combination products for at least 24 hours).

6.1 Screening (Visit 1), Study Day -31 to -1

The following assessments and procedures should be completed in the order given below, if possible:

- Collect signed and dated ICF, Health Insurance Portability and Accountability Act (HIPAA) Form, and Experimental Research Subject's Bill of Rights (if appropriate for that region).
- Receive a 6-digit patient number
- Review inclusion and exclusion criteria
- Record medical history and demographics
- Vital sign measurements
- Record height and body weight
- Review and record prior and concomitant medications
- CT Scan (only required for subjects that are enrolled at Study Sites that are approved and qualified to perform CT Scans)
- NCS assessment
- VAS-rhinosinusitis assessment
- SNOT-22 assessment
- TNSS assessment
- Nasal endoscopy and NPS scoring
- Spirometry (Baseline pulmonary function test) and reversibility testing if documentation of $\geq 12\%$ reversibility is not available in the prior 12 months
- Complete physical examination
- 12-lead ECG
- Hepatitis & HIV Screens
- Pregnancy test (Blood collection for pregnancy test for female patients of childbearing potential at Visit 1 then urine pregnancy tests at subsequent visits)
- Safety laboratory tests (hematology, serum chemistry, urinalysis)
- Dispense and instruct eligible patients on the proper use of the handheld device to capture NPIF, patient diary of symptoms (rhinorrhea etc), concomitant medication use.
- Sites may also provide MFNS for required concomitant use
- Dispense optional take-home rescue medications (albuterol/salbutamol) to asthma patients, if needed. Instruct patients to document the use of albuterol/salbutamol in their patient diary.

- AE review and recording

Screen failures should be recorded in the eCRF but they do not need to undergo all assessments listed for the Early Termination Visit. The Early Termination Visit assessments should be performed with patients if they withdraw from the study after randomization.

6.2 Baseline Visit (Visit 2), Study Day 1

The following assessments and procedures should be completed in the order given below, if possible:

- Review patient diary and NPIF data; retrain patient on proper diary use, if necessary
- Review and record prior and concomitant medication
- Vital sign measurement
- Record weight
- NCS assessment
- EQ-5D-5L questionnaire
- VAS-rhinosinusitis assessment
- SNOT-22 assessment
- TNSS assessment
- UPSIT assessment of smell
- Nasal endoscopy and NPS scoring
- Pulmonary function tests (Spirometry) for patients with comorbid asthma only
- Healthcare Resource Utilization Questionnaire
- Brief physical examination
- 12-lead ECG
- Urine pregnancy test for female patients of childbearing potential
- Safety laboratory tests (hematology, serum chemistry, urinalysis)
- PK blood sample (predose)
- ADA blood sample (predose)
- PD blood sample (predose)
- Verify eligibility.

- Randomization
- Administer study drug
- Injection site assessment
- Dispense optional take-home rescue medications (albuterol/salbutamol) to patients with asthma, if needed. Remind patients to document the use in their patient diary.
- AE review and recording

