- n. PK blood samples should be collected prior to dosing; date and clock time for each sample should be recorded.
- o. PD blood samples for biomarkers of inflammation include Eotaxin-3, eosinophil cationic protein, total immunoglobulin E, thymus and activation-regulated chemokine, and periostin. Blood eosinophil count will be measured as part of hematology test. C-reactive protein will be determined as part of the serum chemistry.
- p. ADA blood sample: NAb will be tested at all ADA collection time points in samples that are ADA positive.

Suzhou Connect Biopharmaceuticals, Ltd

Protocol CBP-201-WW003

Investigational Drug: CBP-201

21 December 2021

- q. Patients are to be observed for 2 hours postdose on D1 (V2), W2 (V4), and W4 (V5), and 30 minutes postdose for W6 (V6) and beyond. Assessments and testing should be completed predose except as noted otherwise. Rotate injection sites: abdomen (avoid area proximal to umbilicus), outer thigh, and upper arm (lateral or posterolateral). Only 1 mL should be injected per site, and an injection site should not be in the same anatomical location used during the previous visit.
- r. Dispense albuterol/salbutamol MDI for reversibility testing and as an optional take-home rescue medication for those patients with asthma. Patients should be offered replacements as needed for symptom control throughout the study and should be reminded to document the use in their patient diary. Sites may also provide MFNS for required concomitant use as needed.
- s. Injection site reactions should be assessed at all visits from the first dosing day until the end of the study. The previous injection site(s) should be assessed prior to dosing. On all dosing days, the new injection site should be assessed prior to the patient's release. The SC injection site may be assessed using a standard instrument provided in Appendix or described as needed by the Investigator in the medical notes. Clinically significant findings as determined by the Investigator will be reported as an AE. See section 8.6 for more details.
- t. Unscheduled visits may be conducted as needed, and additional assessments performed at these visits are at the discretion of the Investigator.
- u. CT scan will only be required for subjects that are enrolled at Study Sites that are approved and qualified to perform CT Scans.

Suzhou Connect Biopharmaceuticals, Ltd

Protocol CBP-201-WW003

Investigational Drug: CBP-201

21 December 2021

LIST OF ABBREVIATIONS

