7.7 Pregnancy Test

A pregnancy test will be performed for female patients of childbearing potential at the timepoints specified in the Schedule of Assessments ([Table 1](#)). A serum pregnancy test will be performed at the Screening visit and a urine pregnancy test will be performed at all visits thereafter. A negative pregnancy test result must be obtained prior to randomization. Additional or more frequent pregnancy testing may be performed if required by local regulations.

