7.8.5 Computed Tomography (CT) Scan

Sinus CT scanning is used to assess fluid-filled or thick-membraned sinuses, to assess the extent of inflammation, to assess polyps and other growths in the airway, and to create a “map” of the patient’s sinus cavities. An Imaging Manual will be provided separately to Study Sites that are approved and qualified to perform CT Scans. The Imaging manual will detail the equipment settings and requirements for scanning. The Imaging Manual will also detail the radiologic scoring of CT scans. All scans will be reviewed by blinded central over-read. Lund-Mackay Computed Tomography qualitative scores and quantitative analysis will be performed from patients enrolled at Study Sites that are approved and qualified to perform CT scans.

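### At Screening the sinus CT is listed ten items before the pregnancy test, and no available text requires a negative result before the scan

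*Protocol*

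**What the plan says.** Protocol 6.1 introduces the Screening list with an ordering rule: "The following assessments and procedures should be completed in the order given below, if possible". Item 8 is the "CT Scan (only required for subjects that are enrolled at Study Sites that are approved and qualified to perform CT Scans"). Item 18 is the "Pregnancy test (Blood collection for pregnancy test for female patients of childbearing potential at Visit 1 then urine pregnancy tests at subsequent visits").

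The deadline for the result is in Protocol 7.7: "A negative pregnancy test result must be obtained prior to randomization". Table 1 footnote i says the same. Inclusion criterion 7 asks for a negative serum test at Visit 1 but does not place it before or after the CT.

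Two places govern the CT. Table 1 footnote u says only "CT scan will only be required for subjects that are enrolled at Study Sites that are approved and qualified to perform CT Scans". Protocol 7.8.5 refers the technical detail to a separate document: "The Imaging manual will detail the equipment settings and requirements for scanning". Neither mentions pregnancy.

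Protocol 7.7 leaves room for further tests: "Additional or more frequent pregnancy testing may be performed if required by local regulations".

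**The concern.** The CT is a study procedure that exposes the patient to radiation. The test that would reveal a pregnancy is already planned for the same visit, but the stated order puts it after the scan. The requirement for a negative result attaches to randomization at Visit 2, so it cannot protect a scan done at Visit 1.

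At stake is research imaging of a woman with an unrecognised pregnancy. If one were then found, Protocol 4.7 would treat her as a screen failure with no further follow-up required once she is withdrawn, although 8.9 asks for any female patient's pregnancy to be reported within 24 hours. She could therefore leave the study after the scan with a report made but no outcome followed. No endpoint, test or sample-size figure is affected.

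**Working it through.** The plan gives no figure to reproduce. The check is a count of list positions and a comparison of the rules that could put a test before the scan.

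**Positions in Protocol 6.1.** Consent is item 1, criteria review 3, CT 8, pregnancy blood draw 18. The test comes 18 − 8 = 10 items after the CT and 18 − 3 = 15 items after the criteria review. Study pregnancy tests before the Screening CT, if the list is followed: 0.

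**Could another rule close the gap?**

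| Rule | Place | Does it act before the Screening CT? |
|---|---|---|
| Negative result before randomization | 7.7, footnote i | No; randomization is at Visit 2 |
| Negative serum test at Visit 1 | Inclusion 7 | Not ordered relative to the CT |
| Pregnant women excluded | Exclusion 22, reviewed at item 3 | Only for a known pregnancy; the study's own sample is not yet drawn |
| Contraception from consent | Inclusion 7 | No; it cannot rule out conception before that visit |
| Extra testing under local regulations | 7.7 | Depends on the site's jurisdiction |
| Scanning requirements | Imaging Manual, via 7.8.5 | Unknown; the manual is not available |

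**Contrast with the later CTs.** The CT also precedes the urine test at Week 24 (6.15: CT item 6, test item 17) and at Early Termination (6.19: CT item 4, test item 16). The exposure there is much smaller:

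- By Table 1 and the Section 6 lists, the tests before Week 24 fall at Screening and on Days 1, 29, 57, 85, 113 and 141, which makes 7. The last is 169 − 141 = 28 days before the scan. With the ±3-day windows the gap runs from 166 − 144 = 22 to 172 − 138 = 34 days.
- Protocol 7.7 also says "a urine pregnancy test will be performed at all visits thereafter". Read literally, that gives 14 tests (Visits 1 to 14), the last on Day 155, 169 − 155 = 14 days before the scan (166 − 158 = 8 to 172 − 152 = 20). The same section ties testing to Table 1, so the count of 7 is the more natural reading.
- Early Termination applies only after randomization, so a negative result has already been required.

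At those visits contraception is also already in force. Only at Screening is the number of prior study tests zero.

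**The case against.** The strongest objection is that the absence is judged without the Imaging Manual. Protocol 7.8.5 sends the scanning requirements there, and it is the natural home for a pre-scan pregnancy check. This stands as a limit: the available text shows no requirement, which is not proof that sites had none.

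Second, the list order is soft. It is qualified, and the protocol overrides it elsewhere: 7.8.1 wants endoscopy at the end of the visit, yet 6.1 lists it 13th, ahead of spirometry, ECG and the blood draws. Screening spans Days −31 to −1, and nothing forces the CT onto the same day as the blood draw or ahead of it. All true, so a site is free to test first. But endoscopy has a specific instruction that corrects the list, and the available text has none for the CT.

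Third, Protocol 11.10 binds the investigator to national, state and local law. Where that law requires a check before imaging, the check is mandatory. The documents do not show whether such rules exist at every site across the US, China, the European Union and the Eurasian Economic Union, so this gives no uniform protection at protocol level.

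Fourth, the practical value is low. SAP 4.15 records early termination and leaves both CT measures out even of the efficacy listings, and no document shows a Screening CT still to be done. This stands, and it is the main reason to keep the weight low.

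**Conclusion.** The concern holds as a low-weight patient-safety point. Followed as written, the Screening list puts the CT ahead of every study pregnancy test, and no available text makes a negative result a condition of the scan. The counts are certain: items 8 and 18, with zero prior tests.

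The consequence is not sized. The documents do not give the radiation dose, the number of women of childbearing potential, the number of CT-approved sites or the turnaround time of the serum test. The conclusion assumes that a site follows the listed order and that neither the Imaging Manual nor local rules already require a check. Because the trial was terminated early, the point matters mainly for any remaining screening and for a later protocol that reuses this list. The Week 24 and Early Termination order is a minor matter.

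**What to change.** In Protocol 6.1, move the pregnancy test above the CT. Reordering alone is not enough, because the Visit 1 test is a blood draw whose result may not be back that day. So add one sentence to 7.8.5 or to Table 1 footnote u: at CT sites, a woman of childbearing potential needs a negative pregnancy result before the scan, and at Screening either the serum result or a same-day urine test will do. If the Imaging Manual already says this, a cross-reference and the reordering suffice. As an optional tidy-up, move the scheduled urine test above the CT in 6.15 and 6.19.

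The drafting cost is one sentence and one reordered list, or three lists with the tidy-up. The operating cost depends on the route:

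- **Urine test:** one added test at Screening per woman of childbearing potential at a CT site.
- **Serum result:** no added test, but a deferred scan and possibly an extra trip for each such woman whose result is not back that day.

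A deferred CT must still be done and read before randomization, because exclusion 15 depends on it, and the run-in can be as short as 7 days. Coming back on another day is already accepted for lung function testing (4.6). SAP Table 2 accepts a baseline CT from Day −30 to Day 1, so the analysis window is unaffected.
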